7.1.7. Additional Analysis of Adverse Events

7.1.7.1. Cardiovascular Events

Proportion of subjects with adjudication-confirmed cardiovascular events will be summarized by treatment group for the Randomized and OL Phase. Multiple events will be counted only once per subject in each summary for each phase. All adjudicated cardiovascular events will be listed for All Randomized Analysis set.

Time to the first cardiovascular event will be assessed in Randomized Phase. Time (in months) to the first cardiovascular event/censoring date will be calculated as: $(\text{first cardiovascular event date or censoring date} - \text{randomization date} + 1) / 30.4375$. Censoring date will be the latest date among the last visit date in the Randomized Phase, the latest AE onset date in the Randomized Phase, the day prior to OL Study Day 1 for subjects discontinued from the Randomized Phase, and the data cut date for ongoing subjects in the Randomized Phase (for the Week 48 Interim Analysis only).

For the purpose of analysis, if the onset date of a cardiovascular event or an AE is incomplete, the first day of the month (if date is missing) or the first day of the year (if date and month are missing) will be used to derive the first cardiovascular event/censoring date. If such imputation leads to an imputed event date that is earlier than the randomization date, then the randomization date should be used to impute the incomplete event date.

Proportional hazards model will be used to calculate the point estimate and 95% CI for the hazard ratio between SEL 18 mg (SEL 6 mg) and placebo controlling for stratification factors.

For each treatment group, KM estimates of cardiovascular event probability at 3-month intervals (ie, at Month 3, 6, 9, etc) and 95% CIs will be provided. The 95% CIs will be calculated based on Greenwood's formula and log-log transformation of the survival function.

Median, Q1 and Q3 of the time to the first cardiovascular event will be provided for each treatment group. The 95% CI for median EFS based on Brookmeyer-Crowley method {[Brookmeyer 1982](#)} of inverting a generalization of the sign test for censored data will also be provided for each treatment group.

7.2. Laboratory Evaluations

Laboratory data collected during the study will be analyzed and summarized using both quantitative and qualitative methods. Summaries of laboratory data will be provided for the (OL) Safety Analysis Set as appropriate and will include data collected up to the last dose of any study drug in the Randomized/OL Phase plus 30 days for subjects who have permanently discontinued study drug in the Randomized (and before the first dosing date in the OL Phase)/OL Phase. The analysis will be based on values reported in conventional units. When values are below the LOQ, they will be listed as such, and the closest imputed value will be used for the purpose of calculating summary statistics as specified in Section 3.7.

A by-subject listing for laboratory test results will be provided by subject ID number and visit in chronological order for hematology, serum chemistry, and coagulation separately. Values falling outside of the relevant reference range and/or having a severity grade of 1 or higher on the CTCAE severity grade as described in [Appendix 2](#) will be flagged in the data listings, as appropriate.

No formal statistical testing is planned.

7.2.1. Summaries of Numeric Laboratory Results

Alanine aminotransferase, AST, albumin, ALP, glucose, total bilirubin, direct bilirubin, GGT, HOMA-IR, HbA1c, and INR in the Randomized Phase will be summarized as efficacy endpoints. Descriptive statistics will be provided by treatment group for ALT, AST, albumin, ALP, glucose, total bilirubin, direct bilirubin, GGT, HOMA-IR, HbA1c, and INR in the OL Phase, and creatinine, creatinine clearance (Cockcroft-Gault), white blood cells (WBCs), neutrophils, lymphocytes, hemoglobin, and platelets in the Randomized/OL Phase as follows:

- Baseline value
- Value at each postbaseline visit
- Change from baseline at each postbaseline visit

Change from baseline at a postbaseline visit will be defined as the visit value minus the baseline value in the corresponding study phase. The mean, median, Q1, Q3, minimum, and maximum values will be displayed to the reported number of digits; SD values will be displayed to the reported number of digits plus 1.

Baseline and postbaseline CP score in the OL Phase will be summarized by counts of subjects and percentages at each category level. Change from baseline will be summarized in the following 3 ordered categories: improvement, no change, and worsening. Worsening refers to an increase in the score, and improvement refers to a decrease in the score.

Median (Q1, Q3) of the observed values for WBC, neutrophils, lymphocytes, hemoglobin, and platelets will be plotted using a line plot by treatment group (1, 2, and 4) and visit for the Randomized Phase.

In the case of multiple values in an analysis window, data will be selected for analysis as described in Section 3.8.3.

7.2.2. Graded Laboratory Values

The CTCAE Version 5.0 will be used for assigning toxicity grades (0 to 4) to laboratory results for analysis. Grade 0 includes all values that do not meet the criteria for an abnormality of at least Grade 1. For laboratory tests with criteria for both increased and decreased levels, analyses for each direction (i.e., increased, decreased) will be presented separately.

For the baseline ALT, AST, total bilirubin and direct bilirubin toxicity grades of each phase, the CTCAE version 5.0 will be used to assign grades to the derived average values.

7.2.2.1. Treatment-Emergent Laboratory Abnormalities

Treatment-emergent laboratory abnormalities are defined as values that increase by at least 1 toxicity grade from baseline at any postbaseline time point in the corresponding study phase, up to and including the date of the last dose of study drug plus 30 days for subjects who permanently discontinued study drug (and before OL Study Day 1 for abnormalities in the Randomized Phase), or the last available date in the database snapshot for subjects who were still on treatment at the time of an interim analysis. If the relevant baseline laboratory value is missing, any abnormality of at least Grade 1 observed within the time frame specified above will be considered treatment emergent.

7.2.2.2. Treatment-Emergent Marked Laboratory Abnormalities

Treatment-emergent marked laboratory abnormalities are defined as values that increase from baseline by at least 3 toxicity grades at any postbaseline time point, up to and including the date of the last dose of study drug in the corresponding study phase plus 30 days for subjects who permanently discontinued study drug (and before OL Study Day 1 for abnormalities in the Randomized Phase) or the last available date in the database snapshot for subjects who were still on treatment at the time of an interim analysis. If the relevant baseline laboratory value is

missing, any Grade 3 or above values observed within the timeframe specified above will be considered treatment-emergent marked abnormality.

7.2.2.3. Summaries of Laboratory Abnormalities

Laboratory data that are categorical will be summarized using the number and percentage of subjects in the study with the given response at baseline and each scheduled postbaseline visit for the Randomized/OL Phase.

The following summaries (number and percentage of subjects) for treatment-emergent laboratory abnormalities will be provided by laboratory test and treatment group; subjects will be categorized according to the most severe postbaseline abnormality grade for a given laboratory test:

- Graded laboratory abnormalities
- Grade 3 or 4 laboratory abnormalities
- Marked laboratory abnormalities

For all summaries of laboratory abnormalities, the denominator is the number of subjects with nonmissing postbaseline values up to 30 days after the last dosing date (and before OL Study Day 1 for the Randomized Phase) of the reporting phase.

A by-subject listing of treatment-emergent Grade 3 or 4 laboratory abnormalities will be provided by subject ID number and visit in chronological order. This listing will include all test results that were collected throughout the study for the laboratory test of interest, with all applicable severity grades or abnormal flags displayed.

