#### Chemistry:

ALT, AST, albumin, ALP, bicarbonate, blood urea nitrogen (BUN), calcium, chloride, creatinine, glucose, magnesium, phosphorus, potassium, sodium, total and direct bilirubin, total protein, uric acid and GGT.

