### Additional Tests:

HIV-1 (reflex to HIV-1 RNA), HBV (HBsAg), HCV (reflex to HCV RNA) serology, urine drug screen (for amphetamines, cocaine, methadone, opiates), homeostasis model assessment of insulin resistance (HOMA-IR, based on fasting glucose and insulin), eGFR as calculated by Cockcroft-Gault, C-peptide, lipid panel, insulin, free fatty acids, digoxin (for those taking digoxin), creatine phosphokinase, and HbA1c (or serum fructosamine if HbA1c is unable to be resulted).

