#### **7.5. Toxicity Management**

At baseline, some subjects may have liver biochemistry levels above the upper limit of normal (ULN). Baseline values for liver tests (ALT, AST, and total bilirubin) will be determined by averaging the values obtained at Screening and Day 1.

If no other cause of the laboratory abnormalities is immediately apparent, on-treatment elevations of ALT and/or AST should be confirmed with repeat testing within 48-72 hours. Subjects with ALT or AST elevations as per [Figure 7-1](#) must be placed into close observation (as described below).

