**Close observation includes:**

- Repeating liver biochemistries (ALT, AST, ALP, GGT, total bilirubin, INR) and obtaining a creatine phosphokinase (CPK) level within 48-72 hours of results
- Obtaining a more detailed history of symptoms and prior or concurrent disease
- Obtaining a history of concomitant drug use (including nonprescription medications and herbal and dietary supplement preparations), alcohol use, recreational drug use, and special diets
- Obtaining a history of exposure to environmental chemical agents
- Ruling out other causes of liver disease as needed (obtain viral hepatitis panel, imaging for evaluation of biliary tract disease, etc. if required in the opinion of the primary investigator)
- Continue to monitor liver biochemistries at least twice weekly. Frequency can decrease to once a week or less if abnormalities stabilize or study drug has been discontinued and the subject is asymptomatic

During close observation, study drug can be continued, if desired, at the discretion of the Gilead Medical Monitor and the Principal Investigator.

If on-treatment elevations of ALT and/or AST exceed the values shown in Figure 7-2, are confirmed on repeat testing within 48-72 hours of results, and no alternative cause is immediately apparent, the subject must be placed into close observation and study drug must be withheld.

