- g For subjects with questionnaires available at Day 1
- h Adverse Events reporting during Screening is limited to serious adverse events and adverse events related to study procedures
- i Additional testing: digoxin level at Day 1 and Week 1 and as needed in subjects taking digoxin (refer to Section 5.4) and CPK level for subjects in close observation for DILI (refer to Section 7.5)
- j Females of childbearing potential only (refer to Appendix 3). Serum pregnancy test at Screening and urine pregnancy test at Day 1 and every 4 weeks thereafter. Starting at the Week 48 visit, urine pregnancy testing kits will be provided for home testing every 4 weeks, between in-clinic study visits. All females of childbearing potential will be contacted every 4 weeks and asked to report the result of the urine pregnancy tests. FSH testing as per Appendix 3

- k To be performed during the Randomized Phase in all subjects and during the OL Phase, only in subjects with severe hepatic impairment (Child-Pugh Class C) in combination with renal impairment (eGFR < 30 mL/min)
- l To be performed during the OL Phase, only in subjects with severe hepatic impairment (Child-Pugh Class C) in combination with renal impairment (eGFR < 30 mL/min)
- m **CCI**
- n For specific blood volumes at each visit, please refer to the current approved ICF
- o Subjects prematurely discontinuing from the study should complete an ET visit within 30 days of last dose, Follow-Up visit 4 weeks later and a Telephone Follow-Up visit after the ET visit
- p To be performed 12 weeks after the Week 240/EOT or ET visit. At the discretion of the investigator, an unscheduled visit may be completed if the subject reports abnormal or concerning symptoms
- q Not to be performed at the Week 144 visit
- r To be performed at the discretion of the investigator
- s Not to be performed at the Week 240/EOT visits
- t To be collected in all subjects that ET in Randomized or OL Phase

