Appendix 2. CTCAE Grade for Laboratory Parameters

CTCAE 5.0	CTCAE Grade				
CTCAE Term	Grade 1	Grade 2	Grade 3	Grade 4	Grade 5
Anemia	Hemoglobin (Hgb) <LLN - 10.0 g/dL; <LLN - 6.2 mmol/L; <LLN - 100 g/L	Hgb <10.0 - 8.0 g/dL; <6.2 - 4.9 mmol/L; <100 - 80g/L	Hgb <8.0 g/dL; <4.9 mmol/L; <80 g/L; transfusion indicated	Life-threatening consequences; urgent intervention indicated	Death
Activated partial thromboplastin time prolonged	>ULN - 1.5 x ULN	>1.5 - 2.5 x ULN	>2.5 x ULN; bleeding	-	-
Alanine aminotransferase increased	>ULN - 3.0 x ULN if baseline was normal; 1.5 - 3.0 x baseline if baseline was abnormal	>3.0 - 5.0 x ULN if baseline was normal; >3.0 - 5.0 x baseline if baseline was abnormal	>5.0 - 20.0 x ULN if baseline was normal; >5.0 - 20.0 x baseline if baseline was abnormal	>20.0 x ULN if baseline was normal; >20.0 x baseline if baseline was abnormal	-
Alkaline phosphatase increased	>ULN - 2.5 x ULN if baseline was normal; 2.0 - 2.5 x baseline if baseline was abnormal	>2.5 - 5.0 x ULN if baseline was normal; >2.5 - 5.0 x baseline if baseline was abnormal	>5.0 - 20.0 x ULN if baseline was normal; >5.0 - 20.0 x baseline if baseline was abnormal	>20.0 x ULN if baseline was normal; >20.0 x baseline if baseline was abnormal	-
Aspartate aminotransferase increased	>ULN - 3.0 x ULN if baseline was normal; 1.5 - 3.0 x baseline if baseline was abnormal	>3.0 - 5.0 x ULN if baseline was normal; >3.0 - 5.0 x baseline if baseline was abnormal	>5.0 - 20.0 x ULN if baseline was normal; >5.0 - 20.0 x baseline if baseline was abnormal	>20.0 x ULN if baseline was normal; >20.0 x baseline if baseline was abnormal	-
Blood bicarbonate decreased	<LLN and no intervention initiated	-	-	-	-
Blood bilirubin increased	>ULN - 1.5 x ULN if baseline was normal; > 1.0 - 1.5 x baseline if baseline was abnormal	>1.5 - 3.0 x ULN if baseline was normal; >1.5 - 3.0 x baseline if baseline was abnormal	>3.0 - 10.0 x ULN if baseline was normal; >3.0 - 10.0 x baseline if baseline was abnormal	>10.0 x ULN if baseline was normal; >10.0 x baseline if baseline was abnormal	-
Cholesterol high	>ULN - 300 mg/dL; >ULN - 7.75 mmol/L	>300 - 400 mg/dL; >7.75 - 10.34 mmol/L	>400 - 500 mg/dL; >10.34 - 12.92 mmol/L	>500 mg/dL; >12.92 mmol/L	-
CPK increased	>ULN - 2.5 x ULN	>2.5 x ULN - 5 x ULN	>5 x ULN - 10 x ULN	>10 x ULN	-

CTCAE 5.0	CTCAE Grade				
CTCAE Term	Grade 1	Grade 2	Grade 3	Grade 4	Grade 5

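### CPK is drawn only for cause and without a scheduled baseline, so any CPK row in the SAP's laboratory abnormality tables would not estimate incidence in the randomised arms

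*SAP*

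**What the plan says.** **Sampling.** The chemistry panel in Protocol 6.11.1 ends with "sodium, total and direct bilirubin, total protein, uric acid and GGT" and does not include CPK. The Additional Tests entry in the same section names it ("digoxin (for those taking digoxin), creatine phosphokinase, and HbA1c") but assigns no visit. Footnote i to the procedures tables (Protocol Appendix 2, repeated in SAP Appendix 1) limits it to a "CPK level for subjects in close observation for DILI". Protocol 7.5 makes it a step of close observation: "obtaining a creatine phosphokinase (CPK) level within 48-72 hours of results".

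**Entry to close observation.** Protocol 7.5 gives two routes. Subjects with on-treatment ALT or AST elevations as per Figure 7-1 "must be placed into close observation". So must subjects with signs or symptoms of liver toxicity that the investigator suspects are drug-related, with no enzyme threshold attached.

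**Analysis.** SAP 7.2.2 grades laboratory results by CTCAE Version 5.0, and SAP Appendix 2 has a row for "CPK increased". SAP 7.2.2.1 deals with absent baselines: "If the relevant baseline laboratory value is missing, any abnormality of at least Grade 1" counts as treatment-emergent. SAP 7.2.2.2 treats any value of Grade 3 or above as marked in the same situation. SAP 7.2.2.3 summarises treatment-emergent, Grade 3 or 4 and marked abnormalities by test and treatment group, and "the denominator is the number of subjects with nonmissing postbaseline values up to 30 days after the last dosing date".

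**The concern.** The denominator and missing-baseline rules suit tests that everyone has at every visit. There, subjects with a post-baseline value are nearly all of the arm, and a missing baseline is an occasional accident. For CPK neither holds. A subject enters the denominator only after an on-treatment event that treatment may influence, and the Randomized Phase baseline is missing by design.

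A reader of the safety tables would see CPK percentages by arm beside those for ALT or platelets and read them the same way, as incidence among randomised and treated subjects. They would instead be proportions among subjects already selected for a possible liver problem, and the arms would no longer be comparable by randomisation. The treatment-emergent label would also state a change from baseline that nobody measured.

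**Working it through.** The plan gives no CPK rate and no expected number tested, so there is no figure to reproduce. The check traces the rules and then shows how the denominator behaves under stated assumptions.

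**1. Is there a baseline?** The visit lists in Protocol 6.2.1 (Screening) and 6.3.1 (Day 1) do not include CPK, and footnote i adds it only for close observation. Close observation follows on-treatment findings. A Randomized Phase baseline could exist only if a site drew CPK unprompted before dosing. In the OL Phase, a CPK value drawn earlier in the Randomized Phase could serve as baseline under SAP 3.8.3, so the gap concerns the Randomized Phase.

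**2. Do for-cause draws reach the tables?** SAP 3.8.2 includes unscheduled visits after first dose when finding the maximum post-baseline grade. They do.

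**3. What does the missing-baseline rule do?** In SAP Appendix 2, CPK Grade 1 runs from above ULN to 2.5 × ULN, Grade 2 to 5 × ULN, Grade 3 to 10 × ULN, and Grade 4 lies above that. Two hypothetical subjects show the effect:
- 2 × ULN before treatment and 2 × ULN on treatment is Grade 1 to Grade 1. With a baseline it is not treatment-emergent; without one it is.
- 2 × ULN before treatment and 6 × ULN on treatment is Grade 1 to Grade 3, a rise of two grades. With a baseline it is treatment-emergent but not marked, since marked needs three grades; without one it is marked.

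**4. How large is the denominator?** Expected number tested = arm size × share entering close observation. Arm sizes are 320, 320 and 160 (Protocol 8.10). The share is not given. Two proxies come from the protocol: pooled Phase 2 liver-test elevations in section 1.5 (17/564 = 3.0% on SEL, 4/182 = 2.2% on placebo) and the 24-week NASH study in section 1.2.7.2 (4/72 = 5.6%). The 10% and 20% rows are assumptions, added because treatment here runs up to 240 weeks.

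| Assumed share tested | Each SEL arm | Placebo | All 800 | One graded placebo subject prints as |
|---|---|---|---|---|
| 3.0% SEL, 2.2% placebo | 9.6 | 3.5 | 22.8 | 1/4 to 1/3 = 25% to 33% |
| 5.6% | 17.8 | 8.9 | 44.4 | 1/9 = 11.1% |
| 10% | 32 | 16 | 80 | 1/16 = 6.25% |
| 20% | 64 | 32 | 160 | 1/32 = 3.1% |

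For one and the same event, the printed percentage depends mainly on how many others happened to be tested.

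**5. How precise would it be?** At the low end, with four placebo subjects tested, exact 95% intervals are 0% to 60.2% for 0/4 and 0.6% to 80.6% for 1/4. With ten SEL subjects tested, 3/10 has an interval of 6.7% to 65.2%. The counts are illustrative only. Even a precise figure at the 20% end would still describe subjects in close observation, not the arm.

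**The case against.** **The CPK row is inferred.** No SAP sentence says that CPK will be tabulated. Appendix 2 is partly a generic CTCAE grid: it also grades lipase and serum amylase, which are not among the protocol's analytes. CPK is absent from the numeric summaries in SAP 7.2.1. This stands, and the point is therefore about what the general rules would produce if applied to CPK. The rules contain nothing to stop that, which is why an explicit exclusion is useful.

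**CPK might be routine.** In Protocol 6.11.1, digoxin is limited to those taking it, while CPK beside it carries no condition. But no visit list calls for CPK, and footnote i gives it a specific condition. The for-cause reading is the better one.

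**The harm is limited.** SAP 7.2 plans no formal testing, SAP 7.2.2.3 already provides a by-subject listing of Grade 3 or 4 abnormalities, and SAP 7.2.4 sends potential DILI cases to adjudication. The missing-baseline rule is a cautious convention that matches Protocol 8.3 and 8.8.3. All of this stands and keeps the point small, but it does not remove a misleading percentage or label.

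**Stronger readings that the documents do not support.** A reader might divide the abnormal count by the full arm and call the result the true rate, so that the SAP percentage looks inflated many times over. That treats every untested subject as having normal CPK, which is unknown. For the same reason, moving the denominator to the Safety Analysis Set would replace one misleading figure with another. A reader might also infer that those tested are selected for high CPK because muscle injury raises liver enzymes. Nothing in the protocol or SAP says so, and the direction of any selection is not established here. Nor is it right to say that testing follows only an ALT or AST rise, given the symptom route in Protocol 7.5.

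**Conclusion.** The point holds in a limited form. If the SAP is followed literally, any CPK row would rest on subjects selected after randomisation and without a planned Randomized Phase baseline. Its percentages would not estimate CPK abnormality rates in the randomised arms, and its treatment-emergent and marked labels would rest on an assumed normal baseline.

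The number tested is an assumption. The range of about 23 to 160 of 800 corresponds to shares of about 3% to 20%. The Phase 2 proxies come from studies with different thresholds, and the pooled ones include other diseases and treatment of 28 days to 48 weeks, so the true number could lie elsewhere. It would be wrong to conclude that only a handful will be tested, or that the printed rates must be high. The conclusion about what the percentages mean does not depend on the share, so long as CPK is drawn only for cause.

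No efficacy endpoint, significance level, sample size or safety rule is touched. This is a minor reporting point.

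**What to change.** Add one sentence to SAP 7.2.2.3: CPK, and any other test drawn only for cause, is excluded from the summaries of treatment-emergent graded, Grade 3 or 4, and marked laboratory abnormalities. Present all CPK results, of whatever grade, in a by-subject listing alongside the DILI evaluation in SAP 7.2.4. Give the number of subjects tested per arm and a note that sampling was for cause and without a scheduled baseline.

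The cost is that sentence and one listing. No new data, visits or changes to subject management are needed.
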